9	MONITORING AND REPORTING OF ADVERSE EVENTS	25
9.1	Adverse Events Definition.....	25
9.2	Suspected Adverse Reaction Definition	25
9.3	Serious Adverse Event or Serious Adverse Reaction Definition.....	25
9.4	Unexpected Adverse Event or Reaction Definition.....	25
9.5	New Fact	26
9.6	Identification of Adverse Events	26
9.7	Follow-up of Adverse Events	27
9.8	Guidelines for Assessing Severity of an Adverse Event.....	27
9.9	Guidelines for Determining Causality	27
9.10	Serious Adverse Events	28
9.11	Unexpected Non-serious Adverse Events.....	28
9.12	Reporting to Health Authority	28
9.12.1	Standard Reporting (IND Annual Report).....	28
9.12.2	Expedited Reporting	28
9.13	Protocol Violations	29
9.14	Reasons for Early Termination	29
9.14.1	Halting the Study	29
9.15	Data Safety Monitoring.....	30
10	STATISTICAL METHODS AND CONSIDERATIONS.....	30
10.1	Analysis Population	30

The SATURN Study [CONFIDENTIAL – DO NOT REDISTRIBUTE]

10.2	Descriptive Statistics.....	30
10.3	Analysis of Primary Endpoints	31
10.4	Analysis of Secondary Endpoints	31
10.5	Analysis of Exploratory Endpoints	31
10.6	Missing Data Handling	32
10.7	Sample Size and Randomization	32
11	DATA COLLECTION, RETENTION AND MONITORING	32
11.1	Data Collection Instruments	32
11.2	Data Management Procedures	33
11.3	Data Quality Control and Reporting.....	33
11.4	Archival of Data.....	33
11.5	Availability and Retention of Investigational Records	34
11.6	Subject Confidentiality	34
12	ETHICAL CONSIDERATIONS	34
12.1	IRB and HIPAA.....	34
12.2	Potential Participant Risks	36
12.3	Potential Benefits	36
13	Abbreviations	36
14	References.....	37

1 **BACKGROUND**

1.1 **Introduction**

This is a prospective, randomized, double-blind, study of H01 of 24 weeks in adults with pulmonary hypertension (PH) with an optional open-label extension (extension to 48 weeks). The primary objective of this double-blinded study is to evaluate the clinical efficacy of H01 over 24 weeks. Secondary objectives are to investigate the safety and tolerability of H01 and pharmacokinetic (PK) and pharmacodynamic (PD) markers in this population. Following IRB approval and written informed consent, a total of 16 participants will be enrolled, randomized approximately 2:1 (H01 1600 mg/day : placebo), stratified by PH type, and treated for 24 weeks. Data from this study will inform future larger studies. Participants will have the opportunity to extend their participation an additional 24 weeks by consenting to an open-label extension.

PH is characterized by remodeling of the pulmonary vasculature, resulting in narrowing and eventual obliteration of the lumen, leading to increased mean pulmonary arterial pressure (mPAP)¹. While multiple therapies have been developed to address PH, there are no disease modifying therapies and morbidity and mortality remains high.

Recent research has suggested that hyaluronan (HA), a key component of the extracellular matrix, plays an important role in the pathology of PH and has potential as a therapeutic target^{2,3}. Hyaluronan is an extracellular matrix glycosaminoglycan capable of trapping large volumes of water and driving pro-inflammatory pathways and fibrosis⁴. The role of hyaluronan in pulmonary hypertension, lung inflammation, and fibrosis has been validated in multiple animal models^{2,3,5,6}. Further, in these models, inhibition of hyaluronan synthesis with H01 led to significant reductions in hyaluronan and had positive effects on clinically relevant outcomes such as Right Ventricular Systolic Pressure (RVSP), the Fulton index and arterial oxygenation (SpO2).

Hymecromone (H01) is a known inhibitor of HA that has been studied in models of respiratory the context of both inflammation and fibrosis. The purpose of this clinical trial is to study the safety and utility of H01 in patients with pulmonary hypertension associated with chronic lung disease (selected from Groups 1 and 3 PH).

We hypothesize that oral H01, at doses of 1600 mg per day, will be a safe and well-tolerated agent in adults with pulmonary hypertension over 24 weeks. In addition, this study will investigate the potential benefit of oral H01 on clinical measures of PH disease severity including but not limited to: pulmonary vascular resistance, mean pulmonary arterial pressure, and the 6 Minute Walk Distance Test (6MWDT).

1.2 Study Overview

Protocol Title	Investigation of H01 in adults with pulmonary hypertension including Interstitial Lung Disease (SATURN Study)
IND #	[REDACTED]
Study Design	Phase 2a, double-blinded, approximately 2:1 randomized and stratified placebo- controlled study to evaluate the safety, tolerability, and efficacy of H01 in adults with pulmonary hypertension (PH), stratified between selected Group 1 and Group 3 PH types with optional open-label extension .
Study Population	Adults with confirmed diagnosis of Group 3 PH secondary to Interstitial Lung Disease(ILD) and Group 1 PH secondary to connective tissue disease, idiopathic, drugs and toxins, or hereditary PAH
Study Drug	400 mg H01 tablets [Isochol 400mg] and placebo
Objectives	
 Evaluate the change in clinical and functional measures in adults with PH treated with H01 Evaluate the safety and tolerability of oral H01 in PH Evaluate the effect of H01 on serum biomarkers in PH
Clinical Phase	2a
Primary Endpoint	
 Change in pulmonary vascular resistance (PVR) measured by right heart catheterization (RHC) from baseline to end of treatment (Week 24) of the blinded study
Secondary Endpoints	
 The safety and tolerability of H01 in adults with pulmonary hypertension using the Common Terminology Criteria for Adverse Events (CTCAE) Change in mean pulmonary arterial pressure (mPAP) by RHC from baseline to end of treatment (Week 24) of the blinded study 6 Minute Walk Distance Test (6 MWDT) from screening to end of treatment (Week 24) of the blinded study and through Week 48 of the open-label extension Change in quality of life (QOL) score, EMPHASIS-10 score and St George Respiratory Questionnaire (SGRQ) score from baseline to end of treatment (Week 24) of the blinded study and through Week 48 of the open-label extension Change in serum HA concentration from baseline to end of treatment (Week 24) of the blinded study and through Week 48 of the open-label extension Change in NT-proBNP from baseline to end of treatment (Week 24) of the blinded study and through Week 48 of the open-label extension
Exploratory Endpoints	
 Change in inflammatory markers (ESR, HSCRP) Change in pro-inflammatory cytokines Change in Forced Expiratory Volume in one second (FEV1) Change in Forced Vital Capacity (FVC) from pulmonary function test (PFT) Change in Total Lung Capacity (TLC) from pulmonary function test (PFT) Change in Lung diffusion capacity (DLCO) from pulmonary function test (PFT) Change in exhaled breath condensate (EBC) hyaluronan concentrations over the study period Describe the pharmacokinetics (H01 and metabolite serum concentrations) Describe HA fragment size

The SATURN Study [CONFIDENTIAL – DO NOT REDISTRIBUTE]

Planned sample size	16
Number of Sites	1
Duration of Participation	
Total study period of the blinded study: 28 weeks
 
Total study period including open-label extension: 48 weeks
 
 ▪ Screening Period: up to 4 weeks ▪ Treatment Period of the blinded study: 24 weeks ▪ Treatment Period including open-label extension: 48 weeks ▪ Follow-up Period: 4 weeks after treatment period ends (Week 24) if not enrolled in the open-label extension
Dose Schedule	
 ▪ Participants randomized to treatment will receive two H01 400 mg tablets BID (1600 mg/day) for 24 weeks or through Week 48 if enrolled in the open-label extension ▪ Participants randomized to placebo will receive two placebo tablets BID for 24 weeks

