2 H01 PHARMACOLOGY

2.1 Dose Rationale

H01 is an approved oral drug in Europe (European Union reference date [EURD] 07/27/1965) for disorders of the biliary tract. H01 has been administered chronically in humans for 50+ years at doses up to 1800 mg/day PO with few observed adverse safety events. Based on the European package insert, the standard dosing regimens for adults in hepatobiliary conditions are 300-600 mg oral up to 3 times / day (900-1800 mg/day).

Several clinical trials of H01 in humans have been published and all demonstrated safety during both short and long-term administration (Appendix B). The longest reported duration of administration was a study of oral administration for 6 months in patients (n=29)⁵⁸. The highest dose administered in a clinical trial is 3600mg for 4 days.

To inhibit excess HA synthesis and alleviate respiratory distress, we propose to administer H01 800mg twice a day (1600 mg/day) PO for 24 weeks. Twice daily dosing was selected to facilitate outpatient adherence. If the participants are enrolled in the open-label extension, H01 is administered twice a day at dose of 800 mg (1600 mg/day) until Week 48.

The selected dose of 1600 mg/day is consistent with non-clinical models of lung injury where human equivalent doses (HED) of H01 ranging from 120 mg/day PO to 2600 mg/day intra-peritoneal (IP) demonstrate notable functional improvements and reduced HA in bronchoalveolar lavage fluid^{2,5,6}. In the Phase 1 dose range study recently completed at Stanford University, doses of 1200mg, 2400mg and 3600mg per day doses over 4 days in healthy volunteers were well tolerated and led to decreases in sputum HA.

Given the existing body of safety data for H01, and the relevance of the models suggesting 2600mg/day IP, characteristics of H01's pharmacology, and the time necessary to see clinical efficacy in pulmonary hypertension patients, the decision was made to target 1600mg/day for 24 weeks. A BID regimen is selected over a QID regimen primarily to support patient compliance over a 24-week period. Participants enrolled in the open-label extension until week 48 will continue this BID regimen (800 mg twice a day).

The results at this dose will inform the H01 development plan and larger scale dose-range studies.

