3.1 Study Treatment

Participants will be randomized approximately 5:3 (Treatment:Placebo). Participants randomized to treatment will be given 800 mg oral H01 two times a day (total dose: 1600 mg/day). Participants randomized to placebo will receive oral tablet placebo (inactive ingredients) two times a day. Participants will be on treatment continuously for 24 weeks or 48 weeks if enrolled in the open-label extension. During the treatment period, participants will be monitored according to the schedule of assessments below. Participant a follow up will take place 30 days after the end of treatment at Week 24 if not enrolled in the open-label extension.

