5.3 Concomitant Medication

To date, there are no known drug-drug interactions for H01. Metoclopramide, its derivatives and morphine are cited in one product label as potentially reducing the effect of H01.

Participants can remain on an FDA approved PAH/PH background therapy if they have been on a stable regimen for a minimum of 90 days prior to randomization.

Participants on a supportive therapy (e.g., anticoagulants, diuretics, oxygen) must have been on a stable and optimized dose for at least 30 days prior to the first dose of study drug. Exceptions are the discontinuation or dose changes of anticoagulants and / or dose change of diuretics. Participants on a chronic medication for underlying lung disease should be on a stable and optimized dose for > 30 days prior to the first dose of study drug.

Participants may not newly initiate PAH/PH treatment from the first dose of study drug (Baseline) through study termination. Participants may not initiate pulmonary rehabilitation (rehab) within 90 days prior to the first dose of study drug and until the end of the study.

All concomitant medications taken during the conduct of the study, including those taken for AEs or other medical events, should be recorded in the subject's source documents and transcribed into the eCRF as required.

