7 ASSESSMENTS

7.1 Screening/Baseline Assessment

Prior to enrollment, each participant will undergo a medical screen, be introduced to study procedures,

The SATURN Study [CONFIDENTIAL – DO NOT REDISTRIBUTE]

and undergo informed consent. Screening will be conducted within 30 days of baseline assessment. If any of the screening labs were performed as part of standard of care within 4 weeks of the screening, these labs will be used for screening.

If the patient qualifies and consents to participate, they will undergo baseline assessments. Baseline labs that were done within the previous 4 weeks will be accepted as baseline labs; if there are no labs for >4 weeks, these will be repeated. If any of the following baseline procedures were performed and documented in the medical chart at part of standard of care within 2 months of the baseline visit, these will be accepted as the baseline assessment: RHC, PFTs, 6MWDT, 12-Lead ECG.

All participants will start taking the study drug on the morning of Day 1, the day after the baseline assessment. All participants will follow up in person for assessments at Weeks 4, 12, and 24. Participants will also be contacted electronically and/or by telephone on Weeks 2, 8, 16, 20, 28. Participants will continue the study drug for 24 weeks with the final in person assessment at Week 24. A final follow-up electronically or by telephone will be performed at week 28 (4 weeks after treatment completion). If participants do not complete the 24 weeks of treatment for any reason, every effort will be made to conduct the Week 24 final assessment at the time of treatment termination and the participant will be followed until at least 4 weeks after stopping the study drug (longer if necessary to follow AEs). If the participants are enrolled in the open-label extension, they will be contacted by telephone on Weeks 26 and 36. A final in-person assessment will occur at Week 48.

Biological samples:

- Blood:
 - 6 ml blood for serum concentration of H01 and metabolites
 - 6 ml blood for serum HA level and biomarkers
 - 6 ml blood for CBC
 - 6 ml blood for CMP
- Urine:
 - Pregnancy test for females of child-bearing potential (serum pregnancy test may be substituted for urine)
- Exhaled breath condensate:
 - Concentration of HA levels, H01 and metabolites

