9.6 Identification of Adverse Events

As all participants in this study will have pre-existing medical conditions, those pre-existing conditions will not be considered adverse events. New events that occur or worsening (through frequency or intensity) of pre-existing conditions will be considered as adverse events.

Adverse events (including SAEs) may be discovered through any of these methods:

1. Observing or interviewing the participant.
2. Procedures / laboratories as performed as part of participating in the study.
3. Receiving an unsolicited complaint from the participant.

The investigator will provide the following information about an AE:

- Date of onset and resolution
- Severity, graded using the NIH Common Terminology Criteria for Adverse Events (CTCAE), Version 5.0
- Action taken with study drug product
- Changes in study drug dosing
- Causal relationship to study drug

- Outcome

All reportable drug adverse events as defined above will be recorded on the appropriate AE/SAE CRF form starting after consent has been obtained until Day 196 (ie at least 30 days after the last dose of study drug).

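### Section 9.6 still ends adverse-event recording at Day 196, and participants who complete the open-label extension have no scheduled off-drug safety contact

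*Combined protocol and SAP*

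**What the plan says.** Section 1.2 sets the follow-up period at "4 weeks after treatment period ends (Week 24) if not enrolled in the open-label extension". Section 3.1 gives the same limit with a slightly different interval: "follow up will take place 30 days after the end of treatment at Week 24 if not enrolled in the open-label extension".

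For those who do enter the extension, section 1.2 states "Total study period including open-label extension: 48 weeks", and gives the treatment period as 48 weeks too. Section 2.1 says "H01 is administered twice a day at dose of 800 mg (1600 mg/day) until Week 48", and section 7.1 says "A final in-person assessment will occur at Week 48". The schedule in section 6 marks Study Termination for extension participants in the Week 48 column and has no later column.

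Section 9.6 opens AE recording at consent and keeps it open "until Day 196 (ie at least 30 days after the last dose of study drug"). It does not mention the extension. The AE row of the schedule, however, is marked for extension participants at Weeks 26, 28, 36 and 48.

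Section 7.1 also requires at least 4 weeks of follow-up after stopping drug, but introduces that rule with "If participants do not complete the 24 weeks of treatment for any reason".

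**The concern.** Safety and tolerability is a secondary endpoint. The AE analysis in section 10.4 defines no time window of its own, so section 9.6 is the text that decides which events are recorded and counted. For extension participants it gives a date that lies well inside the extension, while the schedule tells staff to keep collecting. Sites therefore have two rules.

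Separately, the plan considers one off-drug contact worthwhile after 24 weeks but drops it for people who take H01 for longer. Section 2.1 gives 6 months (n=29) as the longest reported administration, and a participant on H01 from baseline who completes the extension goes to 48 weeks. A new event that begins after that participant's last dose would come to light only through a spontaneous report or in ordinary care.

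**Working it through.** No power or alpha figure is involved. The check is day arithmetic plus a comparison of sections.

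**Where Day 196 comes from.** Inputs: 24 weeks of blinded treatment and 4 weeks of follow-up (1.2).
- Last blinded dose: 24 x 7 = Day 168.
- Plus 4 weeks: 168 + 28 = Day 196, the figure in section 9.6. It is the end of Week 28 of the 24-week design.
- The gloss in the same sentence needs at least 168 + 30 = Day 198. Day 196 gives 196 - 168 = 28 days, so it misses its own definition by 2 days even without the extension.

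**The same rule for the extension.** Input: dosing to Week 48 (2.1).
- Last extension dose: 48 x 7 = Day 336.
- Day 196 precedes it by 336 - 196 = 140 days.
- End of a 30-day tail: 336 + 30 = Day 366. Day 196 precedes that by 366 - 196 = 170 days.
- AE contacts marked for extension participants: Weeks 26, 28, 36 and 48, or Days 182, 196, 252 and 336. The last two of the four fall after Day 196.

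**Scheduled off-drug time, from section 1.2.**
- Not in the extension: 28 weeks in total - 24 weeks on treatment = 4 weeks, with one contact.
- Completing the extension: 48 weeks in total - 48 weeks on treatment = 0 weeks, with no contact.

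**Which day count to use.** From Week 16 the schedule's Day row runs 28 days ahead of 7 x week: Week 16 is 140 against 112, Week 24 is 196 against 168, and Week 48 is 364 against 336. The figures above use 7 x week because Day 196 in section 9.6 was evidently built that way.

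**Other provisions that might fill the gap.**
- 9.7 follows abnormalities attributed to study drug, and 9.14 follows participants who stopped because of an AE. Both concern events already known.
- 9.10 requires serious events to be reported within 24 hours of awareness, with no end date. It depends on someone becoming aware.
- 8.4 asks that people who stop drug stay in follow-up where possible. Someone stopping at Week 30 could still have the Week 36 and Week 48 contacts.
- The 4-week rule in 7.1 is conditioned on not completing 24 weeks, so stopping during the extension lies outside it.

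None of these schedules a contact after the last dose of a participant who completes the extension.

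**The case against.** The strongest reply is that the parenthesis in section 9.6 states the intended rule and Day 196 is a leftover example. With the schedule collecting AEs to Week 48, competent staff would not stop at Day 196. This is fair, and it means that the 140-day and 170-day gaps measure a stale date, not an expected loss of events. But if the parenthesis governs, the protocol requires 30 days of recording after the last extension dose and provides no contact at which to do it.

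A second reply is that the drug is well known. Section 2.1 cites more than 50 years of chronic use at up to 1800 mg/day with few adverse events, and the protocol documents no delayed or withdrawal effect. That stands, and it limits what the extra contact is likely to find.

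Three stronger readings might be inferred, and the documents do not support them:
- *Safety follow-up was not extended at all.* The schedule adds AE and medication collection, laboratory tests and monthly pregnancy tests during the extension.
- *Section 9.6 covers none of the extension, because the schedule places Week 24 at Day 196.* This sets a date built on 7 x week against a Day row that has a separate 28-day shift.
- *Nobody in the extension can have an off-drug contact.* Participants who stop partway may keep the remaining visits under section 8.4.

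In the other direction, Day 364±7 might be taken as a concealed off-drug visit, 21 to 35 days after Day 336. The 28-day shift applies to every column from Week 16, the visit is labelled Week 48, it includes a pill count, and dosing runs until Week 48. It is an end-of-treatment visit.

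**Conclusion.** The point holds in two parts. Section 9.6 is wrong as written for extension participants: its date falls 140 days before a Week 48 last dose, contradicts its own 30-day gloss and contradicts the schedule. And participants who complete the extension have no scheduled off-drug safety contact, against one for those who do not enter it.

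This should be corrected, but it does not threaten the main result. The extension is optional and uncontrolled, and the randomized 24-week comparison is not affected.

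The day figures assume 7 days per week label and dosing through Week 48. They do not depend on which arm a participant came from. The design diagram in section 3 was not legible in the text available, but every readable section agrees that Week 48 is the last extension contact.

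**What to change.** 1. In section 9.6, replace Day 196 with 30 days after the actual last dose of study drug, including any extension dosing. This also removes the 2-day shortfall in the 24-week phase and makes the window independent of the Day row.
2. Add one telephone or electronic contact for AEs and medications 30 days after the actual last dose for every extension participant, including those who stop during the extension. For completers this is Day 366, about Week 52 (366 / 7 = 52.3). Bring sections 1.2, 3.1, 7.1 and the schedule into line.
3. Section 5.3 says "Participants may not newly initiate PAH/PH treatment from the first dose of study drug (Baseline) through study termination" and bars starting pulmonary rehabilitation until the study ends. Add a sentence that, for extension participants, both restrictions still end at the Week 48 assessments, so that the safety call does not prolong them. Nothing else in 5.3 needs to change.

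Cost: at most 16 calls if all 16 participants enter the extension, one schedule column, and one amendment with a consent update. No new procedure or staff is needed. One downside remains: therapy started between Week 48 and the call can make an event found at the call harder to attribute. The medication question at that contact at least records it.

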1.3 Scientific Rationale

1.3.1 *Urgent need for pulmonary hypertension therapeutics*

Pulmonary hypertension (PH) is defined by a pulmonary vascular resistance (PVR) ≥ 3 WU associated with an increased mean pulmonary arterial pressure (mPAP >20 mmHg) at rest¹. It can lead to right ventricle hypertrophy (RVH), right-sided heart failure and eventually death^{7,10}. Idiopathic pulmonary fibrosis (IPF) is a form of restrictive interstitial lung disease (ILD) associated with extremely poor outcomes. IPF is characterized by parenchymal fibrosis that leads to impaired gas exchange⁸. PH, with a prevalence of about 40% in advanced disease^{9,10}, is a common complication in IPF where it is strongly associated with increased morbidity and mortality^{10,11}. It is classified as WHO Group 3 PH¹².

There are limited treatment options for patients with interstitial lung disease and PH, with lung transplantation being the only “curative” option. Despite the many pharmacological agents available to treat pulmonary arterial hypertension (PAH) (classified as Group 1 PH, where no lung parenchymal component is observed), these agents have been shown to be either ineffective or detrimental to patients with IPF + PH¹³. Consequently, it is essential to develop improved medical therapies for IPF+PH.

1.3.2 *Discussion on pulmonary hypertension groups*

This trial selects patients from Groups 1 and 3 PH based on the hypothesized utility of H01 in PH due to lung conditions associated with inflammation, vascular remodeling, and fibrosis. Brief discussion of these groups provides relevant context for selected inclusion/exclusion criteria.

PH is broadly classified into 5 groups based on etiology, although there can also be overlap between groups. Group 1 (also referred to as pulmonary arterial hypertension (PAH)) includes patients with PAH secondary to connective tissue diseases, idiopathic PAH, hereditary PAH, and PAH secondary to selected other conditions (e.g. toxins, HIV, etc.). Although the prevalence of PAH is unknown in North America, several European registries have reported rates of 5 to 52 per million^{14,15}. PAH is a proliferative vasculopathy, characterized by vasoconstriction, cell proliferation, fibrosis, and micro-thrombosis. Pathologic findings include hyperplasia and hypertrophy of all three layers of the vascular wall (intima, media, adventitia) in pulmonary arteries <50 microns (i.e., localizes to the small pulmonary muscular arterioles). In addition, fibrosis and *in situ* thrombi of the small pulmonary arteries and arterioles (plexiform lesions) can be seen^{16,17}. The pathologic appearance of the small pulmonary arteries and arterioles is qualitatively similar in all patients with group 1 PAH.

Over a dozen PAH specific therapies are available. They target components of five PAH relevant molecular pathways: voltage gated, L type calcium channels, nitric oxide cyclic guanosine monophosphate (cGMP), endothelin, and prostacyclin¹⁸. However, effective options for patients with group 1 PAH with *co-existing* lung disease are limited. These patients are primarily treated with

pulmonary vasodilators but outcomes remain poor.

Group 3 PH is the second most common form of PH and is associated with increased morbidity and mortality¹⁹. The most common lung diseases resulting in PH are chronic obstructive pulmonary disease (COPD), interstitial lung disease (ILD) and obstructive sleep apnea (OSA) but PH is also associated with other diseases, such as cystic fibrosis and high altitude exposure. Among the etiologies of group 3 PH, the strongest evidence favors hypoxic pulmonary vasoconstriction (HPVC) with re-modelling of the pulmonary vascular bed. Group 3 PH has a very high morbidity and mortality¹⁹. PH in the setting of fibrotic lung disease is observed in up to 80% of patients with interstitial lung disease (ILD). The presence of PH is considered the single most significant predictor of mortality in patients with chronic lung disease^{10,11}.

The treatment of Group 3 PH has traditionally been to optimize treatment of the underlying lung disease and give long-term oxygen therapy to those who are hypoxic. The efficacy of pulmonary vasodilators in this group of patients is unclear. There have been mixed results from meta-analysis assessing the effects of vasodilators on exercise tolerance and quality of life^{20,21}. Only recently has an acute vasodilator therapy with inhaled treprostinil been evaluated and approved for Group II PH.²²

In view of the poor prognosis associated with these conditions, and the lack of available specific therapy, further work is required to develop effective therapy. The only durable therapy for chronic lung diseases, such as ILD with PH, is lung transplantation. However, lung transplantation itself is associated with inferior outcomes in ILD+PH than for most other indications²³. In addition, despite the many pharmacological agents available to treat pulmonary arterial hypertension (PAH), classified as Group 1 PH, where no lung parenchymal component is observed, these agents have been shown to be either ineffective or detrimental to patients with IPF + PH¹³. Consequently, it is essential to develop improved medical therapies for PH in the setting of chronic lung diseases such as ILD.

